make 80% of all health care decisions for the family, shared the SSE brochure with relatives.^{4,6,29,30}

The *long-term goal* of this research is to reduce melanoma mortality by improving self-management of early detection of melanoma. Reduced mortality cannot be proven without effective structured melanoma SSE with partner assistance. One way to achieve partner-assisted SSE is to deliver a uniform self-management program to women who self-identify as at-risk, perform SSE and seek appointments with HCPs for concerning moles. In the absence of ready physician access due to COVID-19, we will test the feasibility of at-home mole self-sampling with a non-invasive adhesive patch used to acquire surface cells of the mole. Our *primary objective*, assessing effectiveness of a SSE education with partner assistance among at-risk women, extends the evidence-based SSE intervention developed among melanoma survivors and their skin check partners (R01CA154908)⁶ and delivers the program to women who had a screening mammogram, which demonstrated the individuals' commitment to health promotion and cancer screening.

STUDY ENDPOINTS:

Aim 1

Primary outcome:

Effectiveness of TMD with SSE will be defined as SSE performance. Further measures of fidelity will be assessed by:

- a) extent of body checked,
- b) recruitment of a skin check partner,
- c) time between noticing a concerning mole, requesting a mole self-sampling kit, and seeking HCP care for a concerning mole, and
- d) SSE sustained by monthly performance over 4 months.

Secondary Outcome:

The effect of TMD with SSE on seeking health care comparing intervention vs control groups for:

- a) inappropriate HCP appointments and skin biopsies for benign conditions, and
- b) appropriate HCP appointments for the clinical diagnosis of atypical (dysplastic nevus) or rule out melanoma and biopsy performed.

Exploratory Aim

Proof-of-concept Outcome:

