Contact information for potential subjects, who will be women who had a screening mammogram from January 2, 2019 until February 28, 2020, will be obtained from the Northwestern Medicine Electronic Data Warehouse (EDW). Based on our experience, women with a history of breast cancer will be excluded because the focus of their health care is on treatment of breast cancer. Subjects will be emailed a recruitment email explaining the research study regarding skin cancer prevention and skin self-examinations. Subjects will receive a link to the online REDCap program that offers electronic consent, randomization, and self-reported surveys. After remotely enrolling in the study, and completing the baseline questionnaire, the subjects will be randomized 1:1 between intervention and control arms. Intervention arm participants will receive the SSE brochure. The SSE brochure discusses basic information about melanoma, how to identify a melanoma, the importance of a skin check partner, and gives a diary for tracking monthly changes in moles via a provided scorecard. The provided postcard maybe printed by the woman and affixed to a location in their homes to capture their attention and remind participants to perform SSE. Subjects will invite a skin check partner to help score the border, color, and diameter of a new and/or concerning mole(s) using a provided scoring system for their 4 months of study participation. While a skin check partner will be beneficial to perform SSE, a skin check partner is not an absolute requirement to participate in this research. The scoring system uses a scale of 1-3 (1= normal, 2= unsure, 3= not normal). In the brochure, color examples of normal and abnormal features illustrate the scoring rules. The decision rules about seeking health care are based on the cumulative score of three features of the mole: 3 = benign, stop checking the mole; 4-7 = check the mole in one month; 8-9 = make an appointment with a doctor to have the mole checked in about 2-3 weeks, which is the standard of care for evolving moles. In the absence of physician access (COVID-19), the decision rules used in our prior research will be modified to:
8-9= perform mole self-sampling to determine if the mole needs to be biopsied.

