If the option to see the HCP is selected, the research team will assist with locating one and will remind the subject that the HCP may not be available for some time. The study team will not cover the cost of seeing the HCP or cost of treatment recommended by the HCP. The non-payments details are explicitly stated in the consent document.

If the mole(s) requires a biopsy and/or treatment, the EHR will be reviewed to identify diagnosis codes of the mole and review HCP notes.

If throughout the 4 months of active engagement in skin self-examinations, a participant in the intervention arm indicates that they found a concerning mole on their skin check partner while performing a partner skin exam, an opportunity for the concerning mole of the partner to be self-sampled will be offered. For the self-sampling to occur, the subject (the skin check partner) would first be asked eligibility questions to ensure they are over the age of 18 and meet basic eligibility criteria. Once eligibility is established, the partner will be sent an electronic consent form, via REDCap, and complete and sign the form,

indicating they understand what is expected of them as a research participant and the information that was presented to them in the consent document. The same process will be followed for the skin check partner as is in place for the research subject.

Controls (Group 1) will receive a healthy lifestyle brochure and a healthy lifestyle postcard after consenting online and completing baseline assessments. After enrolling in the study, a baseline survey will populate in REDCap, and the subject will be able to download a healthy lifestyle brochure and the postcard reminder. Upon request, the brochure will be mailed. Each month, the subject will receive an email to complete the monthly survey and will receive healthy lifestyle text messages to their mobile phone. The survey they receive will mirror the survey of the SSE intervention arm; therefore, awareness of SSE will be expected to increase, and SSE may be initiated among controls. If a subject indicates that they have found a concerning mole on their monthly survey, the subject will be advised to reach out to their health care provider for further assessment. After completing the final monthly survey, controls will be offered the SSE brochure.

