In order to complete this research before the end of the grant (March 2021), we need to have IRB approval in early May, which will allow EDW to build the lists of eligible subjects. Then we will enroll subjects remotely in June-August 2020 and follow them for 4 months with online surveys (Oct-Dec 2020). Finally, the EHR of HCP visits will be reviewed about 3-4 months after the completion of the last online survey. This additional period of EHR review (Feb 2021- March 2021) gives subjects time to obtain an appointment with their HCP and have a biopsy, if needed.

INCLUSION AND EXCLUSION CRITERIA:

Inclusion Criteria:

- Adult women (aged 18 and older) having a screening mammogram with no upper age limit, who had a screening mammogram from January 1, 2019 to February 28, 2020.
- Able to read English
- Vision enough to read a newspaper
- Self-perception of their potential melanoma risk
- Willing to perform SSE with a skin check partner
- Willing to complete monthly surveys for 4 months and receive monthly text messages to personal mobile phone
- Have home Internet access and smartphone with data plan
- Have access to Federal Express or US Postal Service Express Mail to send mole self-sampling kits
- Willing to allow the research team access to their electronic health record to abstract physician assessment of concerning moles, biopsy results and treatment
- Willing to provide up-to-date email address, mailing address and telephone number

Inclusion criteria of skin check partner to have mole self-sampled

- Male or female over the age of 18 years
- Able to read English
- Vision enough to read a newspaper

Exclusion criteria

- Women under the age of 18 years

- Women overburdened with other co-morbid diseases, medical treatments (e.g., chemotherapy), or cognitive impairment (e.g., by a stroke) as determined by the PI.
- Previous participation in SSE research previously which may be a confounding variable in data analysis

Exclusion criteria of skin check partner to have mole self-sampled

- Male or female under the age of 18
- Unable to read English

VULNERABLE POPULATIONS:

This study will not include the participation of vulnerable populations

PARTICIPANT POPULATIONS:

Accrual Number:	Category/ Group:	Consented: Maximum Number to be Consented or Reviewed/Collected /Screened	Enrolled: Number to Complete the Study or Needed to Address the Research Question
Northwestern Medicine: Prentice Women's Breast Center	Women ≥ 18 years old	500	400

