Design, Analysis, and Power Calculation with Target Enrollment Justification

For the RCT, participants will be randomly assigned to receive the SSE intervention or control (healthy lifestyle) in a 1:1 ratio. This will result in approximately 500 participants in each group. The primary analysis will be intent to treat, with data imputed one of two ways. First, we will run a “worse-case scenario” where all drop-outs will be assumed to not be performing SSE. Second, we will create 5 imputed data sets for missing data based on all available data and analyze with PROC MIANALYZE to obtain valid statistical inferences. From previous work, we expect at least 60% retention at 4 months.

We will use GLMM with a logit link to test if the intervention affects the rate of SSE, while adjusting for the repeated measures within individuals over the first 4 months. Using these repeated measures, and assuming an autocorrelation of 0.9, a total sample of 1000 would enable us to detect an increase from 80% of SSE in the control group to 86.3% in the intervention group. Assuming only 10% discordance, a sample of 500 control women provides 80% power to detect an increase of 7%, while the remaining 3% cease SSE. Additional fidelity measures in Aim 2 will be combined to score an overall standardized fidelity score at each time. If the mean fidelity score is 80%, a sample of 500 women provide enough information to produce a 95% Confidence interval with a width of 0.09. The sample for 500 intervention women provides 80% power to detect declining fidelity or sustainability of monthly SSEs as a standardized slope of 0.13. The secondary outcome of seeking HCP appointments for a necessary mole will be analyzed with generalized linear models, as described above, but considering the outcome as “any HCP appointment” during the study time frame. Previous data suggests that approximately 14% of women should contact HCP for an appointment, and our sample of 1000 women provides 80% power to detect a baseline rate in the control group as small as 21%.

Plans for securing the data is in the “provisions to protect the privacy interests of participants” section of the protocol.

PROVISIONS TO MONITOR THE DATA TO ENSURE THE SAFETY OF PARTICIPANTS:

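### Controls are offered the SSE brochure at month 4, but HCP visits and biopsies are read from the EHR some 3-4 months later with no cut-off, so the secondary comparison between arms can be contaminated

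*Combined protocol and SAP*

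**What the plan says.** Study Interventions makes the brochure the main educational component: "Intervention arm participants will receive the SSE brochure". It explains how to recognise a melanoma and carries the mole-scoring scheme. In the form used in earlier research, the rule for a high-scoring mole was to "make an appointment with a doctor to have the mole checked in about 2-3 weeks"; for the pandemic this is modified to self-sampling.

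Procedures Involved gives controls a healthy lifestyle brochure at baseline, then adds: "After completing the final monthly survey, controls will be offered the SSE brochure".

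Study Timelines says that "the EHR of HCP visits will be reviewed about 3-4 months after the completion of the last online survey", and that the added period "gives subjects time to obtain an appointment with their HCP and have a biopsy, if needed". No distinction is made between arms.

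The Secondary Outcome under Study Endpoints is "The effect of TMD with SSE on seeking health care comparing intervention vs control groups for" inappropriate appointments and biopsies on the one hand, and appropriate ones on the other. The analysis section (Design, Analysis, and Power Calculation with Target Enrollment Justification) analyses it by "considering the outcome as “any HCP appointment” during the study time frame". The time frame is not defined there or elsewhere.

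**The concern.** The control arm is offered the central intervention material at the start of the period in which visits and biopsies can still accrue for the secondary outcome. A control woman who examines her skin because of the brochure, finds a mole and sees a provider can be counted as a control event, although the intervention material prompted the visit.

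The plan does not end control counting at the offer, restrict events to moles reported before it, defer the brochure, or provide a sensitivity analysis. After month 4, contact is limited to incomplete survey items and questions arising from the records, so no scheduled survey would show afterwards which control visits the brochure had prompted.

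At stake is the only planned randomised comparison of care-seeking, including whether SSE education produces needless visits and biopsies. That harm signal could be blurred as easily as the benefit.

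**Working it through.** **1. Overlap in time.** Surveys end October-December 2020 and EHR review runs February-March 2021 (Study Timelines). The interval from brochure offer to review is therefore about 2 months (December to February) to 5 months (October to March), which brackets the stated 3-4 months. The randomised period is 4 months.

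**2. The plan's own figure.** The analysis section claims 80% power with 1000 women for 14% against 21%. Alpha is not stated; I assume 0.05 two-sided, with 500 per arm. With d the difference, p̄ the mean rate and q = 1 − p:

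power = Φ{ [d√n − 1.96√(2p̄q̄)] / √(p₁q₁ + p₂q₂) }

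- d√n = 0.07 × 22.36 = 1.565
- 1.96√(2 × 0.175 × 0.825) = 1.053
- √(0.14 × 0.86 + 0.21 × 0.79) = 0.535
- power = Φ(0.957) = 83.1%

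Eighty per cent power needs 462 per arm, or 490 (980 in total) with continuity correction. The plan's statement reproduces.

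**3. If the intervention raises visits (control 14%, intervention 21%).** Let the late brochure close a fraction f of the 7-point gap. Extra control women with a visit = 500 × 0.07 × f. The values of f are assumptions.

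| f | Extra control women per 500 | Control rate | Power, 500 per arm | N per arm for 80% |
|---|---|---|---|---|
| 0 | 0 | 14.0% | 83.1% | 462 |
| 10% | 3.5 | 14.7% | 74.0% | 579 |
| 20% | 7 | 15.4% | 63.1% | 745 |
| 25% | 8.75 | 15.75% | 57.3% | 854 |
| 50% | 17.5 | 17.5% | 28.9% | 1991 |

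**4. If controls have the higher rate.** The power sentence attaches the 21% to the control group. With 14% in the intervention arm, 10 extra control women per 500 (2 points) move the contrast from 7 to 9 points and power from 83.1% to 95.7%. The observed effect is then inflated.

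**5. If there is no true difference (14% in both arms).** The same 2 points in controls alone give about a 14% chance of a significant result in that direction, against a nominal 2.5%.

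**The case against.** **Later visits may not have been meant to count.** The added period can be read as time to complete care for moles already reported. Procedures Involved and Study Timelines tie record review to the concerning mole(s), and a control who first finds a mole after month 4 has no survey on which to report it. The undefined time frame might also mean the 4 months of engagement. This stands in part: that such visits count is an inference, not a stated rule. But no text excludes them, and the 4-month reading sits poorly with extending the record review so that later appointments and biopsies can occur.

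**Controls do not receive the full intervention.** A reader might infer that the comparison becomes one of early against delayed SSE education. The documents do not support that. Controls are offered a brochure; no SSE reminders, goal-setting surveys, sampling kit or navigation is described for them after month 4. The mirrored monthly surveys are already expected to raise their SSE awareness, so the brochure's added effect may be small.

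**Gross counts mislead.** It is tempting to apply 14% per 4 months to controls who take up the brochure. With 60% retention, 50% use and 3 months, that gives 500 × 0.6 × 0.5 × 0.14 × 0.75 = 15.75 women, or 3.15 points. But the documents give no time base for the 14%, and this gross count cannot be set against a net 7-point contrast. If 14% is what controls would do anyway, users at 14% add nothing. If the brochure moved users from 14% to 21%, the net figure is 500 × 0.6 × 0.5 × 0.07 × 0.75, about 8 women or 1.6 points, still on assumed uptake and timing. This objection stands, and no estimate of actual contamination is offered here.

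**Conclusion.** The point holds as a weakness of the secondary comparison: the plan as written allows brochure-prompted control visits to be counted as control events. The primary outcome is measured before the offer and is untouched.

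The size cannot be determined from the documents. The power figures show sensitivity only: if the intervention raises visits, 7 extra control women per 500 take power from about 83% to about 63%. They rest on two-sided alpha 0.05, 500 per arm, no continuity correction and an assumed fraction of the gap closed.

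A reader might conclude that the arms are necessarily pulled together. That is not supported: dilution follows only if the intervention raises visits, and on the literal wording of the power sentence the contrast widens. Nor do the documents show that contamination will occur, only that nothing prevents it.

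**What to change.** **Preferred.** Move the control brochure offer to after EHR collection closes, for example by sending it with the end-of-study email summary already planned for all participants (Sharing Results with Participants). This changes one sentence in Procedures Involved and adds no patients or procedures. Controls wait about 3-4 months longer for the brochure.

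**If the offer stays at month 4.** Define the study time frame in the analysis section. For the main secondary analysis, count HCP visits dated up to 4 months after randomisation, identically in both arms, and make no brochure offer before that date. Report later visits separately as a sensitivity analysis. The cost is that some late visits and biopsies for moles found earlier leave the main comparison.

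A calendar date is better than a rule based on when a mole was first noticed or on the final survey date. The plan expects only at least 60% retention, so up to 40% of women may have no month-4 survey. The date of noticing rests on self-report, which may differ between women taught to score moles and women who were not.

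Under either option, state which arm the 14% and the 21% belong to, so that the direction of any residual bias can be judged.

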STU#: 00212165

PROTOCOL TITLE: Targeted Melanoma Detection with Skin Self-Examination During COVID-19 Restricted Physician Access

PRINCIPAL INVESTIGATOR:

[name]
Northwestern University Feinberg School of Medicine
Department of Dermatology
[name]
[name]
[contact]
[contact]

RESEARCH PERSONNEL:

[name], MS
[name], BS

STATISTICIAN:

[name]
Professor of Preventive Medicine
Northwestern University Feinberg School of Medicine

VERSION DATE:

April 2, 2020

NCT04420273

STUDY SUMMARY:

The purpose and overarching aim of this study is to reduce melanoma mortality by improving early detection of melanoma with skin self-examination among people who self-identify as being at risk. Self-management of melanoma detection with skin self-examination (SSE) depends on ready access to dermatologists when a concerning mole is detected. In March 2020, the Illinois stay at home order (COVID-19) removed ready physician access and prohibited non-essential health care. Additionally, there was uncertainty about when regularly scheduled health care would resume. This submission seeks to explore the feasibility of at-home non-invasive mole self-sampling for those with a concerning mole with the intention of providing recommendations about the need for the mole to be biopsied.

OBJECTIVES:

Aim 1: To assess the effectiveness of targeted melanoma detection (TMD) with SSE education delivered remotely to women who had a screening mammogram.

The effect of TMD with SSE education on a) SSE performance, b) identification of concerning moles, c) time between noticing a concerning mole, requesting a mole self-sampling kit and receiving health care, and d) SSE sustainability in comparison with controls will be assessed among women served by Northwestern Medicine in one rural community and one metropolitan community. Health care providers' (HCPs) clinical/pathologic assessment of concerning moles will be identified in the Northwestern Medicine electronic health record (EHR) system.

Exploratory Aim: To assess the feasibility of self-sampling concerning moles for gene assay.

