In our prior research, women have checked moles of family members, especially the male spouse. We will extend the opportunity for the women enrolled in the study to sample the concerning moles of their skin check partner. If throughout the 4 months of the intervention arm's active engagement in skin self-examinations, participants indicate that they found a concerning mole on their skin check partner while performing a partner skin exam, an opportunity for the mole of the partner to be self-sampled (or sampled by the participant) will be offered. For mole self-sampling to occur, the subject would first be asked eligibility questions to ensure they are over the age of 18. Once the age is established, the partner will be required to sign an electronic consent form, indicating what information will be collected and what information will be shared with them and their HCP.

Participants who have selected the self-sampling kit will be invited to participate in a structured telephone exit interview. The exit interview will seek to obtain feedback from the participant on the process of self-sampling and gain feedback on study materials.

PROCEDURES INVOLVED:

Enrollment to intervention or control arms, randomization, will be automated in REDCap using a specific formula generated by the performed Northwestern University's Department of Preventative Medicine statistical team. The randomization of subjects who had screening mammograms at Northwestern Medicine Kishwaukee Community Hospital Breast Center and Northwestern Medicine Lynn Sage Comprehensive Breast Center will continue until about 500 women are enrolled from each location. De-identified data will be reviewed by the study's statistical team to ensure there is an equal distribution of subjects at each site in both the intervention and control arm.

In the intervention arm (Group 2), the participant will receive the SSE brochure and SSE postcard after consenting online and completing baseline assessments. Upon request,

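### The primary GLMM adjusts only for repeated measures; prespecifying baseline SSE and site is a cheap improvement to a valid analysis, with a gain the documents cannot fix

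*Combined protocol and SAP*

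**What the plan says.** The section Design, Analysis, and Power Calculation with Target Enrollment Justification gives the primary model as a "GLMM with a logit link to test if the intervention affects the rate of SSE, while adjusting for the repeated measures within individuals". No other section names a covariate for it.

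The material for adjustment is largely in place:

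- **Baseline data.** Study Interventions says that, after enrolling and "completing the baseline questionnaire, the subjects will be randomized 1:1 between intervention and control arms". The items of that questionnaire are not listed, so it is not shown that it records SSE.
- **Site.** Objectives describes "women served by Northwestern Medicine in one rural community and one metropolitan community". Under Procedures Involved, randomisation "will continue until about 500 women are enrolled from each location", and the statistical team reviews the data "to ensure there is an equal distribution of subjects at each site in both the intervention and control arm". Stratified allocation is not stated.
- **Missing data.** The design section is intent to treat with two approaches: drop-outs set to not performing SSE, and a plan to "create 5 imputed data sets for missing data based on all available data". On attrition it says: "From previous work, we expect at least 60% retention at 4 months". The Participant Populations table gives 800 under "Number to Complete the Study or Needed to Address the Research Question".

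**The concern.** SSE before randomisation is a natural predictor of SSE afterwards. If it is recorded, leaving it out gives up precision at almost no saving. Site is known for every woman and its balance is already monitored, but it does not enter the model.

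Three things are at stake. Adjustment can raise power in a trial whose sample leaves little slack. It removes chance baseline imbalance from the estimate. Naming the covariates in advance also removes the temptation to choose between adjusted and unadjusted models after the data are seen.

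**Working it through.** **Inputs from the design section:** control rate 80%, intervention rate 86.3%, 1000 women at 1:1 (500 per arm), autocorrelation 0.9, four monthly measures. **Assumed:** two-sided 0.05, because alpha is not stated for this test; 80% power, which is stated only in the next sentence; AR(1) structure.

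**1. The plan's own figure.** The variance of a four-visit mean relative to one visit is

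f = [4 + 2(3×0.9 + 2×0.81 + 0.729)]/16 = 0.881.

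Exchangeable correlation gives (1 + 3×0.9)/4 = 0.925. Power = Φ(0.063/SE − 1.96), with SE² = (0.80×0.20 + 0.863×0.137)×f/n = 0.2782×f/n. At n = 500, SE = 0.0221 and power is 81% (79% if exchangeable). The rate detectable at 80% power is 86.2% under AR(1) and 86.4% if exchangeable. The stated 86.3% reproduces without any covariate.

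**2. Unadjusted power with fewer women and complete data.** At n = 400 (the table's 800 completers), SE = 0.0248 and power is 72%. At n = 300 (60% of 500), SE = 0.0286 and power is 60%.

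**3. What r might be.** The 0.9 is the correlation among follow-up measures and cannot stand in for r. Two indirect guides exist, and they disagree.

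- Background gives annual community SSE of 8 to 21%. With a baseline rate pb and 80% at follow-up, the largest possible r is √[pb×0.2/(0.8×(1−pb))]: 0.15 at 8% and 0.26 at 21%. A monthly rate below these annual rates would give a lower maximum.
- The discordance sentence has 7% gained and 3% ceasing. If that ran from baseline to an 80% follow-up rate, baseline would be 80 − 7 + 3 = 76%, with 73% performing at both. Then r = (0.73 − 0.76×0.80)/√(0.76×0.24×0.80×0.20) = 0.71. The sentence does not name its time points.

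**4. Adjusted power.** Replace f by f − r² (variance ratio 1 − r²/0.881):

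| r | 400 per arm | 300 per arm |
|---|---|---|
| 0 (unadjusted) | 72% | 60% |
| 0.15 | 73% | 61% |
| 0.26 | 75% | 63% |
| 0.50 (assumed) | 85% | 74% |
| 0.71 | about 97% | about 92% |

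Regaining 80% needs r of about 0.39 at 400 per arm and 0.58 at 300. If r = 0.50 held only at month 1 and decayed by 0.9 a month, 85% would become 82%.

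Simulation with a logistic model and woman-level robust variance (3000 trials, 400 per arm) gave 71 to 72%, 73 to 75%, 73 to 78% and 71 to 83% at r = 0.15, 0.26, 0.36 and 0.50. A random-intercept GLMM (600 trials, Monte Carlo error about 2 points) gave 78 to 79%, 73 to 76%, 71 to 75% and 76 to 85%. These agree in direction. The GLMM figures are the noisier set.

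**5. Under the planned missing-data approaches** (500 per arm randomised in the worst-case runs; drop-out completely at random assumed).

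- Drop-outs set to no SSE, r up to 0.50: power 41-43% at 80% completion, gain 1-3 points; 22-25% at 60% completion, gain 0. If drop-out is spread over the months, the gains reach at most 6 and 4 points.
- Five imputed data sets, 20% with no follow-up (500 trials): no gain at r = 0.26 (71% and 68%, within simulation error); 66 to 72% at an assumed 0.36; 69 to 82% at an assumed 0.50.

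**6. Site alone.** An assumed site difference d explains a share (d/2)²/0.16 of the variance: 0.004 at 5 points and 0.016 at 10 points. At 400 per arm that adds about 0.2 and 0.8 points of power.

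**7. Chance imbalance.** A 1-SD baseline imbalance at 400 per arm moves the unadjusted difference by r×0.4×√(2/400): 0.4 to 0.7 points at r = 0.15-0.26 and 1.4 points at 0.50, against a target of 6.3.

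**The case against.** The strongest reply is that this is a preference. Randomisation already protects the comparison, and at the r values tied to the community rates the gain is 1-3 points before any imputation. Those values are maxima, reached only when every baseline performer also performs at follow-up. That is separation, where the baseline coefficient has no finite estimate. Baseline SSE may not be recorded, site is worth almost nothing, and imputing from all available data may already use both variables.

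Most of this stands. It limits the size of the benefit and means that the separation case needs a rule fixed in advance. It does not remove the case for naming covariates beforehand when doing so costs a sentence and at most one item.

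A reader might infer more than the documents support:

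- **That the unadjusted analysis is biased or underpowered as written.** It is not biased for lack of covariates, and 86.3% reproduces.
- **That 72% and 60% are the power of the planned analyses.** They describe 400 and 300 women per arm with complete data. The plan imputes drop-outs, and 60% is a floor on retention.
- **That adjustment would make up for drop-out.** Under the worst-case approach it barely helps.
- **That 0.71 is the plan's value for r.** The discordance sentence does not say which occasions it compares.
- **That the design obliges a site term.** Balance by site is reviewed, but stratification is not stated.

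**Conclusion.** The point holds as a recommended, low-cost improvement to a valid primary analysis. The omission is plain in the text; the benefit cannot be settled from it. On complete data at 400 per arm the gain runs from 1-3 points of power (r = 0.15-0.26) through 13 points (r = 0.50, assumed) to about 25 points (r = 0.71, one reading). It could also be nil. Nearly all of any gain would come from baseline SSE.

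The figures rest on two-sided 0.05, AR(1) correlation of 0.9 across four visits, a linear approximation to the logit model, and a constant r. Confidence is medium: high that no covariate is named, low on how much adjustment would deliver. The advantage that does not depend on r is that the model is settled before the data are seen.

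**What to change.** - Prespecify baseline SSE (yes/no) and site as fixed effects in the primary GLMM under both missing-data approaches, and name both in the imputation model so that their inclusion is explicit.
- Confirm that the baseline questionnaire records SSE. If it does not, add that one item before the first randomisation.
- Fix a rule for separation. For example, if all baseline performers also perform SSE at every follow-up, keep the term and use a penalised (Firth-type) fit, so that no model choice is left until after the data are seen.
- Report an adjusted risk difference beside the odds ratio.

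The cost is plan wording and at most one online survey item; sample size and visit schedule do not change. The downsides are that the gain may be nil and that the odds ratio, already subject-specific in a GLMM, also becomes conditional on baseline SSE and site. Site-stratified allocation is optional and not needed here. The change does not replace a restatement of power for the expected retention.
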